Rexon-Eye device for the treatment of dry eye

[name], [name], [name], [name], [name], [name]

[name], MD

Ophthalmology Department, Shamir Medical Center, Zerifin, Israel

Email: [contact]

Address: [name].

[contact]

[contact]

Scientific background

Dry eye disease is a highly prevalent and disabling disorder, which affects 9 million persons in the United States alone (1). Affected individuals can have considerable reduction in quality of life and suffer from decreased visual function, social and physical functioning and workplace productivity (2). Available treatments include administration of artificial tear substitutes, suppression of ocular inflammation and treatment targeted at improving meibomian gland function and eyelid hygiene. These treatments all have limited efficacy and dry eye remains a chronic and debilitating disease and an area of unmet medical need.

The Raxon Eye device (Resono Ophthalmic Inc., Trieste, Italy) is a new device based on QMR technology. Quantum Molecular Resonance (QMR) is a technique in which low-intensity, high-frequency electric currents are administered to a biological tissue through contact electrodes. The device applies stimulation to the epidermis of closed eyelids up to the lid margin by means of specially designed goggles. Previous studies have shown that it is relatively safe with high patient satisfaction (3). Preliminary studies have also shown it is effective for accelerate healing in chronic wounds and for treating symptoms of dry eye (4,5).

Possible harms and adverse events

One previous study reported no adverse events related to treatment (5). A second study reported adverse events related to the use of the Raxon device in three cases (3/25, 12%). Two patients showed mild cutaneous erythema following the first treatment and one patient generically felt uncomfortable during the treatment. Additional reported adverse events were anterior uveitis in one patient within the second month of treatment and one event of conjunctivitis within the second month of treatment. One patient suffered from a seasonal allergy during the last two weeks of treatment. The connection of these events to the treatment could not be ascertained (4).

Description of the proposed research

In this study, we aim to examine the efficacy of the Rexion eye device for the treatment of dry eye signs and symptoms in a randomized double-blind placebo-controlled fashion among a cohort of prospectively recruited patients with dry eye. The control group will receive similar application of treatment with the device goggles disconnected from the device, effectively receiving no treatment. The treatment will be performed by research assistants following thorough instruction by the manufacturing company representatives and/or provided material. Participant will be actively questioned on any harms or side effects in every meeting.

Outcomes will be assessed based on clinical signs (e.g. tear break up time, superficial punctate keratitis, meibomian gland dysfunction, Schirmer test). Symptoms of dry eye will be assessed by validated questionnaires on dry eye symptoms (OSDI).

Informed written consent will be obtained from all participants involved in the study prior to enrolment. The goal of the study is to evaluate the Rexion device as a possible additional treatment option to patients with dry eye or to establish it has no added benefit.

Inclusion criteria:

- Patients above the age of 18 years
- Patients who are willing and able to consent and adhere to the research plan
- Patients diagnosed with dry eye

Exclusion criteria:

- Active infection of the eyelid or periorbital area
- Patients who are pregnant or lactating
- Patients under the age of 18
- Those scheduled for (<30 days) or immediately after (<30 days) ocular surgery (excluding cataract and eyelid surgery)

Methods

- 1) Recruitment of patients with dry eye, at risk for dry eye (e.g. post refractive surgery and post cataract surgery), meibomian gland dysfunction.
- 2) Randomization in a 1:1 ratio for treatment or control groups according to a pre-determined computer-generated randomized sequence.
- 3) Treatment or placebo treatment for one month weekly using the Raxon device by a research assistant.
- 4) Follow-up meeting assessing dry eye symptoms and clinical signs of dry eye.
- 5) Data analysis and report of outcomes.

Recruitment

We intend to recruit 25 patients in each group (total of 50 patients).

Bibliography

1. TFOS DEWS II Clinical Trial Design Report. - PubMed - NCBI [Internet]. [cited 2020 Feb 24]. Available from: <https://www-ncbi-nlm-nih-gov.rproxy.tau.ac.il/pubmed/28736344>

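### The goal sentence offers established absence of benefit as one of two conclusions, but 25 per group cannot reliably rule out a small benefit, and can rule out a moderate one only under favourable assumptions

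*Protocol*

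**What the plan says.** In the protocol, under Description of the proposed research, the goal is "to evaluate the Rexion device as a possible additional treatment option to patients with dry eye or to establish it has no added benefit". These are two alternative conclusions, one favourable and one negative. The same section describes the trial as "randomized double-blind placebo-controlled fashion among a cohort of prospectively recruited patients with dry eye".

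Methods item 2 sets "Randomization in a 1:1 ratio for treatment or control groups". The Recruitment section fixes the size: "We intend to recruit 25 patients in each group (total of 50 patients", with no reasoning for the number.

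Outcomes are several clinical signs, given as examples, plus the OSDI for symptoms ("Symptoms of dry eye will be assessed by validated questionnaires on dry eye symptoms (OSDI"). No SD or relevant difference is given for any of them. On analysis, Methods item 5 says only "Data analysis and report of outcomes".

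**The concern.** A comparison that fails to reach significance is not evidence of no benefit. To establish absence of added benefit, the upper confidence limit for the benefit must lie below the smallest benefit worth having. The goal sentence names that conclusion, and the Recruitment section fixes the number of patients who must support it. The question is whether the two fit.

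If they do not, a null comparison could be written up in the terms of the goal, as established absence of benefit, while its interval still contains a worthwhile one. The Scientific background describes existing treatments as limited in efficacy, so wrongly dismissing an additional option would matter. There are several outcomes, so the misreading could occur on more than one.

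This is not a complaint that the margin or test is missing; those may be in a statistical analysis plan. The goal and the sample size are both set in the protocol itself.

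**Working it through.** **The plan's own figure.** The protocol gives no inputs for its 25 per group, so there is nothing to reproduce. As orientation only: a standard two-group superiority calculation with an assumed difference of 0.8 SD, two-sided 5% and 80% power gives 2 × (1.960 + 0.842)² / 0.8² = 24.5, so 25 per group. The protocol does not say that this was the basis.

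**Inputs.**
- From the protocol: n = 25 per group, 1:1.
- Assumed: SD 1 (outcome in SD units); true effect 0; two-sided 5% (upper limit of the 95% interval) or one-sided 5%; correlation r between baseline and follow-up of 0 (unadjusted), 0.5, 0.7 or 0.8; 25 or 20 analysed per group (0 or 20% dropout); 80% taken as reliable.

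**Formulas.** Standard error: se = √(2/n) × √(1 − r²). Degrees of freedom: 2n − 2, less 1 when adjusted. Half-width of the 95% interval: t(0.975, df) × se. Probability of excluding a benefit m when the true effect is zero: P(T > t_crit), where T is noncentral t with noncentrality m/se.

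**Base case.** n = 25, r = 0: se = √0.08 = 0.283; t(0.975, 48) = 2.011; half-width = 2.011 × 0.283 = 0.57 SD. For m = 0.5, the noncentrality is 0.5/0.283 = 1.77 and the probability is 0.41. The half-width falls to 0.49 SD at r = 0.5 and 0.41 SD at r = 0.7.

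**Probability (%) of excluding a benefit, true effect zero.**

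| n per group | Test | r | 0.2 SD | 0.3 SD | 0.5 SD | 0.8 SD |
|---|---|---|---|---|---|---|
| 25 | two-sided 5% | 0 | 10 | 18 | 41 | 79 |
| 25 | two-sided 5% | 0.5 | 12 | 22 | 52 | 89 |
| 25 | two-sided 5% | 0.7 | 16 | 31 | 68 | 97 |
| 25 | two-sided 5% | 0.8 | 21 | 41 | 82 | >99 |
| 25 | one-sided 5% | 0 | 17 | 27 | 54 | 87 |
| 25 | one-sided 5% | 0.5 | 20 | 33 | 64 | 94 |
| 25 | one-sided 5% | 0.7 | 25 | 43 | 79 | 99 |
| 25 | one-sided 5% | 0.8 | 31 | 54 | 90 | >99 |
| 20 | two-sided 5% | 0 | 9 | 15 | 34 | 69 |
| 20 | two-sided 5% | 0.5 | 11 | 19 | 43 | 81 |
| 20 | two-sided 5% | 0.7 | 14 | 25 | 58 | 93 |
| 20 | two-sided 5% | 0.8 | 18 | 34 | 73 | 98 |
| 20 | one-sided 5% | 0 | 15 | 24 | 46 | 80 |
| 20 | one-sided 5% | 0.5 | 18 | 28 | 56 | 89 |
| 20 | one-sided 5% | 0.7 | 22 | 37 | 70 | 97 |
| 20 | one-sided 5% | 0.8 | 27 | 46 | 83 | >99 |

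**Ranges over all settings.** 0.2 SD: 9-31%. 0.3 SD: 15-54%. 0.5 SD: 34-90%. 0.8 SD: 69% to over 99%.

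**Size needed.** With r from 0 to 0.7 and either sidedness, 80% probability of excluding 0.3 SD needs 71 to 176 per group, and 0.5 SD needs 26 to 64 per group.

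**The misreading, in numbers.** If the true benefit were 0.5 SD, 59% of trials with 25 per group would be non-significant (two-sided 5%, unadjusted), or 48% and 32% at r = 0.5 and 0.7. If the true effect is zero, 97.5% of two-sided tests do not favour the device. Of those, (0.975 − 0.410)/0.975 = 58% have an interval that still contains 0.5 SD (unadjusted).

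**The case against.** The sentence can be read as plain language for finding out whether the device works; the operative aim in the same section is to examine efficacy in a randomised comparison. A reader might infer that the protocol commits itself to treating a non-significant result as proof of no benefit, or that it rules out an inconclusive report. It does neither: no such rule is written, and the clause is a goal, not an endpoint. The harm is a report that the wording permits.

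A reader might also infer that 25 per group cannot establish absence of benefit at all. That is too strong. The answer depends on what benefit matters, and the protocol does not say. If only a benefit of about 0.8 SD is worthwhile, the goal is largely attainable: 79% in the base case. A moderate benefit of 0.5 SD is excluded with 80% probability or more when the baseline correlation is about 0.8, except at 20 per group with a two-sided test (73%). The margin, sidedness and adjustment could properly be set in a statistical analysis plan.

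Finally, any trial of this size is imprecise for small effects, so the point could be called generic. What makes it specific is that this protocol names a negative conclusion as a goal. No later choice of margin or analysis within the range examined makes exclusion of 0.2 or 0.3 SD reliable: the highest probabilities are 31% and 54%.

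**Conclusion.** The point holds as a mismatch between a stated goal and a stated size. With a truly ineffective device, the trial would usually fail to exclude a 0.2 SD benefit in every setting examined. It would exclude 0.3 SD in about half of trials at best. For 0.5 SD it reaches roughly 80% only with a strong baseline correlation, about 0.7 with a one-sided 5% test and no dropout, or about 0.8 otherwise.

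All of this rests on assumed alpha, SD units, correlation and dropout, and on a true effect of exactly zero. A small true benefit would lower the probabilities and a small true harm would raise them. Severity is minor: one clause overstates what the trial can conclude, and the design itself can stand.

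**What to change.** Reword the goal clause along these lines: to estimate the effect of the device against sham with 95% confidence intervals. Add that a non-significant result alone is not reported as absence of benefit. That conclusion is drawn for an outcome only if the interval lies wholly below a smallest worthwhile difference set in advance for that outcome, in the protocol or the statistical analysis plan. Otherwise the result is reported as inconclusive.

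The cost is a reworded clause with its reporting rule, and a justified smallest worthwhile difference for each outcome on which absence of benefit is to be claimed, and for no others. That takes some work, because the protocol gives no SDs for the OSDI or the signs. Some null results will have to be called inconclusive. If no such claim is wanted, deleting the negative half of the goal is enough. Sample size and outcomes need not change.

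### Does the trial need a written pre-randomisation measurement of OSDI and the clinical signs, given that only the follow-up meeting is timed?

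*Protocol*

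**What the plan says.** The Methods section of the Protocol lists five steps: recruit, randomise, treat weekly for a month, follow up, analyse. The fourth reads "Follow-up meeting assessing dry eye symptoms and clinical signs of dry eye", and no other sentence says when symptoms or signs are measured.

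The outcomes paragraph under the description of the proposed research names the measures without a time. For signs: "Outcomes will be assessed based on clinical signs (e.g. tear break up time, superficial punctate keratitis, meibomian gland dysfunction, Schirmer test". For symptoms: "Symptoms of dry eye will be assessed by validated questionnaires on dry eye symptoms (OSDI". The one item collected throughout is harms: "Participant will be actively questioned on any harms or side effects in every meeting".

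Entry requires "Patients diagnosed with dry eye", with no test or recorded value named. Allocation is described as "Randomization in a 1:1 ratio for treatment or control groups according to a pre-determined computer-generated randomized sequence". The size is given under Recruitment: "We intend to recruit 25 patients in each group (total of 50 patients". The stated goal is to evaluate the device as an additional treatment option "or to establish it has no added benefit".

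**The concern.** Read literally, the order of the steps places the only assessment after a month of treatment. Timing of measurement is a matter of data collection. A statistical analysis plan can choose a model, but it cannot supply a pre-treatment OSDI score that nobody recorded. Without that score the trial could not describe how severe the disease was at entry, see a chance difference between arms, report change, or use the strongest available covariate.

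Two features of this trial sharpen the worry. The arms are small. Step 1 also names a mixed group: patients with dry eye, those at risk after refractive or cataract surgery, and those with meibomian gland dysfunction. Severity at entry may therefore vary widely. And if the result is neutral, a claim of no added benefit depends on how narrow the confidence interval is.

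**Working it through.** **Inputs.** From the Protocol: 25 per group and 1:1 allocation. Assumed, because the Protocol gives none of them: two-sided alpha 0.05, 80% power, all 50 patients analysed, a continuous outcome with one value per patient, and a baseline-to-follow-up correlation r of 0.3, 0.5 or 0.7. The Protocol has no precision or power figure to reproduce. All results are in units of the outcome SD.

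**Bias.** Under randomisation the expected baseline difference is zero, so the difference in follow-up means estimates the treatment effect with or without adjustment. A simulation of 20,000 trials of 25 + 25 with a true difference of 0.60 SD gave an average estimate of 0.60 for both analyses, at r = 0.5 and at r = 0.7.

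**Standard error.** Post-treatment values only: sqrt(2/25) = 0.283. Adjusted for baseline (ANCOVA): 0.283 × sqrt(1 − r²). The simulated values were 0.284 against 0.248 at r = 0.5, and 0.281 against 0.203 at r = 0.7.

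**95% confidence interval half-width** = t(0.975, df) × standard error, with df 48 post-only and 47 adjusted. **Detectable difference** is from the noncentral t distribution.

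| Analysis | Variance relative to post-only | Half-width | Detectable difference |
|---|---|---|---|
| Post-treatment only | 1.00 | 0.569 | 0.809 |
| ANCOVA, r = 0.3 | 0.91 | 0.543 | 0.772 |
| ANCOVA, r = 0.5 | 0.75 | 0.493 | 0.701 |
| ANCOVA, r = 0.7 | 0.51 | 0.406 | 0.578 |

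Estimating the covariate slope inflates the ANCOVA variance by about 1 + 1/46 = 1.022. This moves the three adjusted half-widths only to 0.549, 0.498 and 0.411.

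**Gain from adjustment.** The half-width narrows by 0.569 − 0.543 = 0.026 SD at r = 0.3, by 0.076 SD at r = 0.5 and by 0.163 SD at r = 0.7. To match these precisions, a post-only trial would need 25/(1 − r²) per group: 27.5, 33.3 or 49.0.

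**A baseline does not help by itself.** If it were used as a simple change score, the half-width would be 0.569 × sqrt(2(1 − r)): 0.673 at r = 0.3, 0.569 at r = 0.5 and 0.441 at r = 0.7. For r up to 0.5 that is no better than having no baseline.

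**The neutral result.** With an observed difference of exactly zero, benefits up to 0.57 SD remain possible without a baseline, and up to 0.54, 0.49 or 0.41 SD with one. Half a standard deviation or thereabouts stays open either way at r = 0.3 or 0.5. That limit comes mainly from 25 per group.

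**What the text supports.** The outline lists no procedures of any kind under recruitment, so the absence of OSDI and signs there says little about intent. A follow-up visit presupposes something to follow up from, and a diagnosis of dry eye presupposes an examination. No sentence excludes a baseline or confines outcome measurement to the end.

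**The case for a change.** The strongest case for a change is that the loss, if it happens, cannot be reversed. Once treatment has begun, the outcome's own pre-treatment value is gone. Other covariates would recover only a little, and a larger sample is the only full substitute. The remedy is cheap: one questionnaire and a few routine tests at enrolment. An informal baseline might also use different tests from those at follow-up, or be taken after allocation. With 25 per group, a chance baseline difference of at least 0.3 SD arises in about 29% of randomisations (0.3/0.283 = 1.06 standard errors, two-sided normal tail), and nobody could see or adjust for it. If patients drop out, the main covariate for handling missing outcomes would be absent too.

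Much of this stands. The Protocol is silent, an unseen analysis plan does not cure a measurement not taken, and at r = 0.7 the gain is worth having. But each harm depends on the investigators not measuring at entry what they must largely examine to make the diagnosis, and the text gives no sign of that. Chance imbalance is already covered by the standard error of the unadjusted comparison. The dropout point is real, but the Protocol gives no dropout figure from which to size it. The figures also suit OSDI best, because the Protocol gives no scale for keratitis or meibomian gland dysfunction and does not say how two eyes are handled.

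**Conclusion.** No change to the plan follows. The gap is one of missing detail: the Protocol does not say whether OSDI and the signs are recorded before randomisation, and it does not say that they are not. Investigators running a dry-eye trial with a diagnosis at entry and a later follow-up visit would very likely record them. If they did not, the comparison between arms would still be unbiased with a valid standard error, provided follow-up is complete.

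The cost in that case is precision alone: a half-width of 0.57 SD instead of 0.54 to 0.41 SD, and a detectable difference of 0.81 SD instead of 0.77 to 0.58 SD. These ranges rest on the assumed correlations of 0.3 to 0.7, 5% two-sided alpha, 80% power and all 50 patients analysed. At the low end the difference is negligible. How a baseline would enter the analysis is a modelling choice commonly left to a statistical analysis plan, which is not at hand. Whether a finding of no added benefit is attainable turns mainly on the sample size, and a baseline would not settle it.
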